- All other non-injected lesion(s) that are not treated with CyPep-1 injection.
- For Phase I Cohort 3 and all Phase IIa arms, in addition to iRECIST, (exploratory) ORR in injected and non-injected lesions will be assessed per itRECIST ([Appendix F](#)). For Phase I Cohort 3, Phase IIa Arms A, B, and C, data will be extracted retrospectively from eCRF.

Upon start of CyPep-1 treatment, subjects will be followed for PFS (every 8 weeks) and OS. PFS will be radiologically assessed at the trial sites until disease relapse or progression (based on all lesions), death due to any cause, withdrawal of consent, loss to follow-up, or until the end of the trial, whichever occurs first. A phone call for survival status (OS) will be done every 3 months after confirmation of PD and until the end of the trial.

Confirmation of clinical progressive disease:

In order to account for the possibly delayed onset of CyPep-1 action and for subjects who are of acceptable clinical performance status (as deemed by the investigator), if PD is recorded and provided that the tumor enlargement is smaller than 50% compared to the previous measurement, the subject will remain in the trial and will be reassessed radiologically after 4 weeks. All lesion(s) are to be evaluated for clinical progression:

- If the lesion(s) continue(s) to enlarge, the original PD will be considered as the “first documented PD” and there will be an End of Treatment (EoT) visit.
- If lesion(s) remain(s) unchanged or decrease(s) in size, assessments should continue as per protocol (i.e., the next radiological assessment will be performed after an 8-week interval). In this case, the first measured PD will be disregarded.

In case of unconfirmed PD after the first (or subsequent) 3 Q2W injections of CyPep-1, the subject should continue Q2W administrations (start of another cycle of CyPep-1) until confirmed PD. If PD is confirmed 4 weeks later, then the subject will be taken off-trial and move to the EoT visit.

PHARMACOKINETIC ASSESSMENTS:

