22. Radiological assessment should include chest, abdomen, pelvis and all other known sites of disease. The baseline scan for radiological assessment is to be done within 4 weeks prior to C1V1 (V1 for Arm D). If radiological assessments has been done in clinical routine within 4 week before Visit 1 and scan fulfills requirements for iRECIST (and additionally iiRECIST for Arm D) evaluation, this scan can be used for baseline evaluation (not need to be repeated during screening). Follow-up scans are to be performed every 8 weeks starting C1V1 (V1 for Arm D). The window for follow up radiological assessments during the trial is ± 3 days. Once a tumor lesion(s) is documented, the target area should be recorded at every subsequent time-point for the duration of the trial. Efficacy assessment will be based on RECIST (and additionally iiRECIST for Arm D) for up to 10 target lesions. All skin lesions must be assessed by caliper measurement during clinical exam on the dates corresponding to iRECIST/iiRECIST assessment. Documentation by color photography including a ruler to estimate the size of the lesion should be stored in the patient file.

23. A confirmatory radiological assessment only has to be done if PD was observed with the previous radiological assessment. If the lesion(s) continue(s) to enlarge, the original PD will be considered as the 'first documented PD'. If lesion(s) remain(s) unchanged or decrease(s) in size, assessments should continue as per protocol (i.e., the next radiological assessment will be performed after an 8-week interval). In this case, the first measured PD will be disregarded. In case of unconfirmed PD after the first (or subsequent) cycle, the subject may continue Q2W administrations of CyPep-1 and Q6W administrations of pembrolizumab in the combination arm. If PD is confirmed 4 weeks later, then the subject will be taken off-trial and move to the EoT visit.

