Once a tumor lesion is documented, the target area should be recorded at every subsequent time point for the duration of the trial. The same type of scan should be used in a subject throughout the study to optimize the reproducibility of the assessment of existing and new tumor burden and improve the accuracy of the assessment of response or progression based on imaging.

In order to account for the possibly delayed onset of CyPep-1 action and for subjects who are of acceptable clinical performance status (as deemed by the Investigator), if PD is recorded and provided that the tumor enlargement is smaller than 50% compared to the previous measurement, the subject will remain in the trial until confirmed PD and will be reassessed radiologically after 4 weeks. A confirmatory radiological assessment only has to be done if at the previous visit PD was observed with radiological assessment. If the lesion(s) continue(s) to enlarge, the original PD will be considered as the "first documented PD". If lesion(s) remain(s) unchanged or decrease(s) in size, assessments should continue as per protocol (i.e., the next radiological assessment will be performed after an 8-week interval). In this case, the first measured PD will be disregarded. In case of unconfirmed PD, the subject should stay on treatment with CyPep-1 (plus pembrolizumab in the combination arm). If PD is confirmed 4 weeks later, then the subject will be taken off-trial and move to the end of treatment visit.

Tumor response or progression on CT/MRI will be determined according to iRECIST (modified RECIST1.1 using up to 10 target lesions) and itRECIST [[Goldmacher 2020](#)]). A summary of itRECIST in comparison to iRECIST is in [Appendix F](#).

ORR in all lesions will be evaluated based on the investigator's assessments per iRECIST. ORR in injected and non-injected lesions, separately, per itRECIST will be programmatically calculated using data obtained from iRECIST assessments.

Local measurement of tumor lesion(s)

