For Phase I, and Phase IIa Arms A, B and D: Local measurements of (to-be) accessible injected cutaneous/subcutaneous tumor lesion(s) must be done within one day (<24h) prior to each CyPep-1 injection by caliper and color digital photography, using a ruler held flush to the skin next to the longest diameter of the lesion to indicate the size of the lesion. If needed, guidance with ultrasound is permitted. The (to-be) injected lesions under ultrasound control, must be measured with ultrasound guidance before each CyPep-1 injection only on dates of CyPep-1 injection. All ultrasound and color digital photography image files should be stored and available in the patient file). Lesion(s) that disappeared will be checked on the days of CyPep-1 injection.

Lesion mapping

A lesion map that will guide the preferred sequence of injection of the identified Lesion Sets must be created prior to the first CyPep-1 injection (detailed in Study Procedural Manual). A lesion map will contain the information as described in [Section 5.3.1.3](#).

Once the lesion map is created, lesion sets for sequential CyPep-1 injections will be planned and documented in the source. The size of the injected lesions and the lesion map should be updated when assessments of local measurements of tumor lesions and iRECIST and itRECIST assessments are performed during the treatment period.

End of Treatment and Follow-up Tumor Imaging (Arm B)

If subjects discontinue study treatment, tumor scans should be performed at the time of discontinuation (± 4 -week window) unless previous scans were obtained within 4 weeks of discontinuation. Subjects who are clinically stable and treated past radiographic progression may continue to be assessed until progression is confirmed according to the rules of iRECIST, when clinically appropriate.

If subjects discontinue study treatment without documented disease progression, every effort should be made to monitor disease status by acquiring tumor scans using the same schedule used while on treatment (every 8 weeks in Year 1 or every 12 weeks after Year 1). Scans are to be continued until one of the following conditions are met:

- Disease progression as defined by iRECIST
- The start of a new anticancer treatment
- Pregnancy
- Death
- Withdrawal of consent
- The end of the study

Survival

PFS

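### At the 4-week rescan the protocol body text confirms PD on any further growth, Appendix D requires at least 5 mm or another listed worsening, and nothing says which rule prevails

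*Protocol*

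**What the plan says.** Three places give a two-way rule for the rescan 4 weeks after a first PD: the synopsis (Confirmation of clinical progressive disease), Schedule of Assessments footnote 23, and Section 6.2 (Clinical Response based on iRECIST and itRECIST assessments).

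- Growth: "If the lesion(s) continue(s) to enlarge, the original PD will be considered" the first documented PD. None of the three gives a minimum.
- No growth: "If lesion(s) remain(s) unchanged or decrease(s) in size, assessments should continue as per protocol", and the first PD is disregarded.
- Consequence: the synopsis completes the growth branch with "and there will be an End of Treatment (EoT) visit". Section 6.2 and footnote 23 use a separate sentence: "If PD is confirmed 4 weeks later, then the subject will be taken off-trial".

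Section 6.2 also states: "Tumor response or progression on CT/MRI will be determined according to iRECIST". Its Arm B imaging text says that clinically stable subjects treated past progression "may continue to be assessed until progression is confirmed according to the rules of iRECIST".

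Appendix D sets out those rules. Target-lesion PD is confirmed by a further increase of at least 5 mm in the sum of diameters. Significant non-target growth, listed new-lesion worsening or a new RECIST 1.1 trigger also confirms. If none occurs and the target sum is still above the initial PD threshold, the response stays iUPD with another scan at 4 to 8 weeks. If none occurs and the sum is not above the threshold, it resolves to iSD, iPR or iCR. While PD is unconfirmed, a clinically stable subject continues treatment.

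Section 6.2 and the synopsis attach a condition to staying in the trial for the rescan: "provided that the tumor enlargement is smaller than 50% compared to the previous measurement". Footnote 23 has no such limit ("A confirmatory radiological assessment only has to be done if PD was observed with the previous radiological assessment"), and neither has Appendix D.

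**The concern.** Both rules govern the same decision. Appendix D says that iRECIST guides management as well as scoring, and no text gives either rule precedence. Two sites with the same scans can therefore act differently, each following the protocol.

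The rescan exists because Section 6.2 allows for a delayed onset of CyPep-1 action. A zero threshold works against that aim, since any measured increase, even a millimetre, falls in the confirming branch. If the investigator then records iCPD, SAP Section 10.1.1 stops counting assessments towards best overall response. The 8-weekly PFS visits also end (footnote 4; Section 6.2, PFS), so a later regression would not be seen. The arms are small: in Arm B one subject is 1/15 = 6.7 percentage points of ORR.

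**Working it through.** The plan gives no figure to reproduce, so I applied both written rules to the same scans.

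**Inputs.** PD threshold (Appendix D): at least 20% and at least 5 mm above nadir. Confirmation (Appendix D): at least 5 mm above the first-PD sum. Confirmation (body text): any enlargement, read here as enlargement of the target sum. Assumed for illustration: nadir 50 mm, first PD 62 mm, no non-target, new-lesion or other worsening, and a clinically stable subject.

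Threshold = max(1.2 × 50, 50 + 5) = 60 mm. First PD: (62 − 50)/50 = +24%.

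| Rescan sum | Change from 62 mm | Body text | Appendix D |
|---|---|---|---|
| 58 mm | −4 mm | PD disregarded, continue | Not above 60: resolves to iSD or iPR, continue |
| 61 mm | −1 mm | PD disregarded, continue | Above 60: iUPD persists, continue |
| 62 mm | 0 | PD disregarded, continue | iUPD persists, continue |
| 64 mm | +2 mm (3.2%) | First PD stands, EoT | iUPD persists, continue |
| 66 mm | +4 mm (6.5%) | First PD stands, EoT | iUPD persists, continue |
| 67 mm | +5 mm (8.1%) | First PD stands, EoT | iCPD |

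There are two zones of disagreement. Between 0 and 5 mm of growth, the rules differ on whether treatment stops. For an unchanged or slightly smaller sum still above threshold, treatment continues under both, but the first PD is cancelled under one and remains iUPD under the other. The growth zone is the same at other sums. An increase of 4.9 mm is 16.3% of 30 mm, 8.2% of 60 mm and 4.1% of 120 mm, and at each of these first-PD sums the two rules give different answers.

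**Consequences for endpoints.**

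1. Small growth recorded as iCPD: the best-response window and the PFS visits close.
2. Small growth, treatment stopped, but coded iUPD as Appendix D requires: the window stays open. Footnote 4 keeps PFS visits going until confirmed PD or a new line of therapy.
3. PFS, DOR and duration of stable disease: rows 3 and 4 of SAP Tables 8 and 9 already count several unconfirmed iUPD patterns as events at the progression date. These include iUPD followed by discontinuation for radiological progression, and iUPD followed only by iUPD. For a subject who goes on progressing, the event date is usually the same under either rule.
4. Two differences remain. A subject stopped for radiological progression on small growth is an event under row 3, while one kept on who then regresses is not. In the second zone, if a cancelled PD is coded iSD, row 4 no longer applies and the first PD is no longer the event date.

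**Added treatment.** For a subject kept on as persistent iUPD and confirmed at the next scan, the delay is 4 to 8 weeks. At one dose every 2 weeks that is 4/2 = 2 to 8/2 = 4 doses.

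**The case against.** The best defence is that Section 6.2 and footnote 23 do not send enlargement straight to EoT. They say only that the original PD becomes the first documented one, and a separate sentence conditions EoT on confirmation. With iRECIST named in the same section, a site can read confirmation through Appendix D. A reader might infer that all three places tie growth directly to EoT, but only the synopsis does. The defence still falls short. The only alternative branch covers unchanged or smaller lesions, so small growth has nowhere else to go, and the synopsis removes any doubt about what follows.

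It is also fair that the loss in ORR depends on an investigator recording iCPD contrary to Appendix D, and that these endpoints are secondary or exploratory in a non-randomised trial whose primary endpoints are safety and dose. That limits the weight of the point. Early stopping, however, does not depend on the coding.

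Three stronger readings are not supported:

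- A reader might infer that enlargement of 50% or more gets no 4-week rescan. Section 6.2 and the synopsis do not say what happens then. The text is unclear on this and does not prohibit a rescan.
- A reader might infer that many responses are lost. The documents give no growth rates and no count of subjects who grow slightly and later regress. A subject who keeps growing will in time pass 5 mm, and the conflict then only shifts the stopping date, typically by one scan interval.
- A reader might infer operational harm from Appendix D's two references to a Section 14, when the protocol ends at Section 13. Scan timing is given elsewhere, so this is editorial.

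**Conclusion.** The inconsistency is real and should be corrected. It covers target growth above 0 and below 5 mm with no other worsening, and an unchanged or slightly smaller sum still above threshold. In the first zone it changes when treatment stops. If iCPD is recorded there, it also closes the best-response window and PFS follow-up early. In the second it changes whether a PD is cancelled or stays open as iUPD.

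The number of subjects affected is unknown and may be small. The effect on PFS, DOR and duration of stable disease is limited, though not removed, by SAP Tables 8 and 9, rows 3 and 4. The benefit also depends on how many subjects are still on treatment, which the documents do not state. Phase I is complete, and Arm D stopped recruiting after one subject.

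The disagreement follows from the wording. The lesion sums are illustrative, and the comparison assumes that enlargement means the target sum and that the subject is clinically stable.

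**What to change.** In the synopsis, footnote 23 and Section 6.2, replace both branches with the Appendix D outcomes:

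- iCPD leads to EoT. State whether Appendix D's provision for continuing after sponsor consultation is kept.
- Persistent iUPD continues treatment if the subject is clinically stable, with a rescan in 4 to 8 weeks.
- iSD, iPR or iCR returns the subject to the 8-week schedule.

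A shorter alternative is to state that Appendix D governs confirmation and delete the conflicting sentences. Changing only the growth branch would leave increases below 5 mm without a rule.

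State in all places what happens when enlargement is 50% or more. Whether to keep the limit as a treatment-continuation rule is the sponsor's clinical choice; under Appendix D the visit is iUPD either way. Correct the two Section 14 references.

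The cost is a protocol amendment. It may count as substantial because it changes when treatment stops, and Section 10.6 then requires ethics committee and competent authority approval. The SAP lists two current protocol versions and three countries. For each subject kept on as persistent iUPD, add one further rescan and about 2 to 4 Q2W CyPep-1 dosing visits.

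### Protocol 6.2, the synopsis and SoA footnote 23 drop a first PD that Appendix D would keep as iUPD, and nothing says what to record at the 4-week scan

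*Protocol*

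**What the plan says.** **Disregard rule.** Protocol 6.2, under the heading on clinical response by iRECIST and itRECIST, deals with a first PD in a subject of acceptable performance status. The synopsis (Confirmation of clinical progressive disease) gives the same rule. Both limit it to cases "provided that the tumor enlargement is smaller than 50% compared to the previous measurement". The subject is rescanned after 4 weeks, with two possible results:

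- Growth: "If the lesion(s) continue(s) to enlarge, the original PD will be considered as the" first documented one.
- No growth: "If lesion(s) remain(s) unchanged or decrease(s) in size, assessments should continue as per protocol", and "In this case, the first measured PD will be disregarded".

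Footnote 23 of the Schedule of Assessments repeats both results but carries neither entry condition. It opens: "A confirmatory radiological assessment only has to be done if PD was observed with the previous radiological assessment".

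**Appendix D.** There are three results at the confirmatory scan:

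- Progression is confirmed if the target sum rises by a further 5 mm or more, or on other listed worsening.
- The response stays iUPD if nothing worsens but the target sum is still above the PD threshold.
- It resets to iSD, iPR or iCR only if nothing worsens and the sum is no longer above the threshold.

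**SAP.** Section 10 uses the investigator's iRECIST response at each visit. Sections 10.1.4 and 10.2.2 date progression from an iUPD that is later confirmed. Row 4 of Tables 8 and 9 also counts an unconfirmed iUPD as an event, but only where no iSD, iPR or iCPD follows it. A visit recorded as iSD is an adequate assessment for censoring.

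**The concern.** Persistent iUPD, the middle result in Appendix D, is missing from 6.2, the synopsis and footnote 23. A subject whose sum is stable but still in the progression range has the first PD dropped under one text and kept under the other. 6.2 does not say which iRECIST category belongs on the 4-week visit.

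Because the SAP works from the recorded category, two sites with the same scans could produce different progression dates. That reaches PFS, duration of stable disease and, through Table 8, duration of response. Best overall response could also become iSD where no iSD or better was recorded earlier. SAP 10.2.6 splits subjects at iSD.

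**Working it through.** **1. The texts side by side** (target lesions only, no other worsening)

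| Target sum at 4 weeks | 6.2, synopsis, footnote 23 | Appendix D | Agree? |
|---|---|---|---|
| At or below the PD threshold | First PD dropped | Reset | Yes |
| Above the threshold, not above the first-PD sum | First PD dropped | Stays iUPD | No |
| Above the first-PD sum by less than 5 mm | PD confirmed, if any growth counts as enlarging | Stays iUPD | No |
| Above the first-PD sum by 5 mm or more | PD confirmed | iCPD | Yes |

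Only the second row can move PFS, duration of stable disease or duration of response through the disregard rule. The third row mainly affects treatment: under 6.2 the subject comes off trial, while under Appendix D treatment continues to a further scan.

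**2. Width of the second row.** Assume a nadir and previous target sum of 50 mm. The threshold is 1.2 × 50 = 60 mm.

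- First PD 61 mm (+22%): sums above 60 and up to 61 mm.
- First PD 74 mm (+48%): sums above 60 and up to 74 mm.
- First PD 80 mm (+60%): above 60 and up to 80 mm. This falls outside the cap in 6.2 but inside footnote 23.

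**3. Dates.** SAP 8.4 gives days = date − treatment start + 1, and months = days / 30.4375. A scan at week w falls on day 7w + 1:

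- week 8: day 57 (1.87 months)
- week 12: day 85 (2.79 months)
- week 16: day 113 (3.71 months)
- three months: 3 × 30.4375 = 91.3 days

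**4. One subject through SAP Table 8.** Assume 61 mm at week 8 and again at week 12.

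| Recorded | Consequence for PFS |
|---|---|
| iUPD at both visits, persistent or later confirmed | Event on day 57; no change |
| Week 8 struck out, week 12 iUPD that persists or is confirmed | Event on day 85; still before 91.3 days, so 3-month PFS does not move (no censoring before then) |
| Week 12 iSD, PD at the next calendar scan, later confirmed | Event on day 113, 8 weeks after day 57 |
| Week 12 iSD, no further scan, no death or new therapy | Row 4 fails; row 5 censors on day 85 |

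Table 9 treats duration of stable disease in the same way. Footnote 22 supports the calendar schedule: "Follow-up scans are to be performed every 8 weeks starting C1V1".

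**5. Size in the iSD branch only.** Moving one subject from day 57 to day 113 raises 3-month PFS by 1/n if nobody is censored earlier:

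- n = 9 (Arm A as planned): 1/9 = 11.1 points
- n = 15 (Arm B): 1/15 = 6.7 points
- n = 24 (Cohort 3 plus expanded Arm A): 1/24 = 4.2 points

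**6. What limits the effect.** Row 3 of Tables 8 and 9 has no exclusion for a later iSD. It still dates the event to week 8 if the subject stops for progression or, for PFS, dies within 8 weeks. If the sum later falls to or below the threshold without worsening, Appendix D also resets and the texts converge.

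**The case against.** The best answer is that iRECIST governs. Appendix D opens by giving the investigator iRECIST both for response and for management decisions. The synopsis (Efficacy Assessments), Table 5 and the Arm B imaging text in 6.2 point the same way, and the next paragraph of 6.2 states: "Tumor response or progression on CT/MRI will be determined according to iRECIST". The disregard paragraph can then be read as a stay-on-trial and rescan rule. It drops only the first PD and never tells a site to record iSD. A week 12 sum of 61 mm against a 50 mm nadir is itself in the progression range. There is also general protection: SAP 10.1.1 lists sums beside the iRECIST evaluation, Protocol 9.1 provides data validation and SAP 7.1 a data review meeting.

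Most of this stands, and it is why the effect is small. It does not remove the conflict. None of these places is a precedence clause. The disregard rule sits under the iRECIST response heading, decides which PD counts as the first documented one, and appears three times. A site that follows it literally is following the protocol. The review steps are general; no visible text checks responses against Appendix D. Part of the text adjoining the opening of SAP section 10, and the plans named in Protocol 9.1, were not available, so such a check cannot be ruled out.

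Three stronger readings are tempting and should not be drawn:

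- **That the plan prolongs PFS as a matter of course.** This needs a recorded iSD, which 6.2 does not prescribe.
- **That every sum from the threshold up to 5 mm beyond the first PD moves PFS.** The upper 5 mm is the opposite conflict, which mainly concerns treatment.
- **That the Arm A expansion decision is affected.** Protocol 3.1 and 8.2 count stable disease beyond 16 weeks from its onset. From an iSD at week 12 to PD at week 16 is 4 weeks, so the criterion is not met. Counting from treatment start borrows the origin of a different endpoint (SAP 10.1.4).

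**Conclusion.** The contradiction is real and can be read directly from the protocol. Its reach is limited to 4-week target sums that remain above the PD threshold without exceeding the first-PD sum. Within that window the consequence depends on what the site records: none, a move to day 85 that leaves 3-month PFS unchanged, or, if iSD is recorded, an event about 8 weeks later or censoring.

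PFS is exploratory, and duration of stable disease and duration of response are descriptive secondary endpoints in an unpowered, non-randomised trial. The disregard rule turns iUPD into iSD at most, so ORR is not affected, nor are the primary safety endpoints. The illustration assumes a 50 mm nadir, progression judged on the target sum alone, and calendar scans. The documents do not say how many subjects fall in the window. Severity: minor.

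**What to change.** **Protocol.** In 6.2, the synopsis and footnote 23, state that confirmation, persistence and reset of a first PD follow Appendix D. Unless one of its confirmation or reset conditions is met, the visit stays iUPD with its original date and treatment continues. Give footnote 23 the same entry conditions as 6.2.

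**SAP.** Before database lock, check each investigator visit response by Appendix D against the recorded target sums and the recorded non-target and new-lesion assessments, and query mismatches. Investigator assessment remains the endpoint. For scans already read, only this step helps.

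**Cost.** Wording in three protocol places, one SAP paragraph, some programming and a few site queries. Non-target progression is qualitative, so that part relies on recorded judgements, not sizes. PFS and duration of stable disease may come out slightly shorter, and some subjects with slight growth would stay on treatment until a further scan.
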